#### **5.3.1. Clinical benefit rate (CBR)**

##### **Definition**

Clinical benefit rate (CBR) is defined as the proportion of participants who achieve a confirmed best overall response of CR, PR, or stable disease for at least 24 weeks based on RECIST version 1.1 during the study (and prior to subsequent therapy if any).

##### **Analysis Methods**

The CBR and its 95% exact Clopper-Pearson CI will be calculated.

#### **5.3.2. Disease control rate (DCR)**

##### **Definition**

Disease control rate (DCR) is defined as the proportion of participants who achieve a confirmed best overall response of CR, PR, or stable disease based on RECIST version 1.1 during the study (and prior to subsequent therapy if any).

##### **Analysis Methods**

The DCR and its 95% exact Clopper-Pearson CI will be calculated.

#### **5.3.3. Progression-free survival (PFS)**

##### **Definition**

Progression-free survival (PFS) is defined as the time from the date of the initial dose of study intervention to the date of first documented disease progression as defined in the RECIST version 1.1, or death due to any cause, whichever occurs first.

##### **Analysis Methods**

Kaplan-Meier estimates will be used for analysis, if there are sufficient data.

The censoring method is described in [Table 4](#)

**Table 4: PFS Event and Censoring Method**

Situation	Date of Progression or Censoring	Outcome
Disease progression	Earliest date that indicates disease progression	PFS event
Death	Date of death	PFS event
No postbaseline disease assessment	First dosing date	Censored
Other (eg, withdrawal of consent to study participation, lost to follow-up, start of subsequent anticancer therapy etc.)	Date of last disease assessment prior to withdrawal of consent to study participation, lost to follow-up, start of subsequent anticancer therapy	Censored

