Keys: AR=androgen receptor; β-hCG=beta human chorionic gonadotropin; C1D1=Cycle 1 Day 1; CT=computed tomography; CTC=circulating tumor cell; E2=estradiol; ctDNA/RNA=circulating tumor DNA/RNA; ECG=electrocardiogram; ECOG-PS=Eastern Cooperative Oncology Group performance status; eCRF=electronic case report form; EOT=end-of-treatment; FDG-PET=fluorodeoxyglucose-positron emission tomography; FFPE=formalin-fixed paraffin-embedded; FSH=follicle stimulating hormone; GnRH=gonadotropin-releasing hormone; HER2=human epidermal growth factor receptor 2; HDL=high-density lipoprotein; ICF=informed consent form; LDL=low-density lipoprotein; LH=luteinizing hormone; MRI=magnetic resonance imaging; PK=pharmacokinetic(s); PSA=prostate-specific antigen; q3 cycles=every 3 cycles; ULN=upper limit of normal; T3=triiodothyronine; T4=free thyroxine; TSH=thyroid-stimulating hormone.

Footnotes:

- a. Must sign the ICF before first study-related activity.

- b. Every effort should be made to document radiographic progression, even after discontinuation of treatment for safety or tolerability reasons (eg, AE) but prior to subsequent therapy.
- c. If a participant discontinues study intervention for safety or tolerability reasons (eg, AE), radiographic evaluations must be continued until disease progression but prior to subsequent therapy according to the same schedule as the one of prediscontinuation (every 2 cycles or every 3 cycles beginning at Cycle 13 from Cycle 1 Day 1) unless (s)he withdraws consent for follow-up.
- d. Locally performed. For fasting laboratory assessments, if the participant has not fasted before the visit, the visit may proceed, but the participant must return within 72 hours in a fasted state to provide the necessary sample(s) for the assessments.
- e. Follow-up for survival will continue until death, withdrawal of consent, lost to follow-up or until the end of the study. Deaths regardless of causality will be reported in the eCRF. Serious adverse events that occur after 30 days following the last drug administration thought to be related to study intervention will be collected and reported via the Serious Adverse Event form within 24 hours of discovery or notification of the event and documented (refer to Section 8.3.1).
- f. Fasting state is defined as 8 hours without food or drink, with the exception of water.
- g. A blood sample will be collected at any time between 0.5 to 4 hours after the apalutamide administration.

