Assessment of responses will be performed according to RECIST version 1.1 criteria. RECIST assessments at baseline should be representative of all areas including metastases. At any time disease progression is clinically suspected, tumor assessments should be performed. Irradiated or partially excised lesions will generally be considered not measurable at baseline and will be followed as non-target lesions, except for a lesion that has progressed following local radiation or surgery, provided the investigator and sponsor medical monitor agree it is measurable and will not confound the efficacy evaluation. Additionally, a lesion that was biopsied during screening should only be assessed as a target lesion if a postbiopsy CT confirms that it still meets measurability criteria and is amenable to accurate and reproducible measurement. Tumor response will be reported by the investigator in the eCRF. The following response criteria (according to RECIST version 1.1) are acceptable: CR, PR, stable disease, progressive disease, unevaluable.

A response of PR or CR must be confirmed by repeat assessments ≥ 4 weeks from the initial observation. For a response to qualify as stable disease, follow-up measurements must have met the stable disease criteria at least once at a minimum interval ≥ 6 weeks after the first dose of study agent.

Every effort should be made to document radiographic progression even after discontinuation of treatment for safety or tolerability reasons (eg, AE), but prior to subsequent therapy.

Assessment of responses will be assessed by the investigator as detailed in the Imaging Manual (refer to Section 9 for definitions). All participant scans will be submitted to an independent central radiology review for quality assessment and for the primary analysis. Further details regarding

materials to be forwarded for central quality assessment can be found in the Imaging Manual or Investigator Site File.

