**Table 2: Summary of Selected Analyses at the Interim Analysis**

	Analysis	Analysis Set
Subject Information	Summary of Demographics and Baseline Characteristics	Treated, Response evaluable
	Disposition Information	Treated, Response evaluable

	Analysis	Analysis Set
	Summary of Exposure and Dose Adjustment	Treated
	Summary of Prior SGC Related Therapy	Treated, Response evaluable
	Current General Medical History by System Organ Class (SOC) and Preferred Term (PT)	Treated
Efficacy	Summary of Overall Response Rate Including Supplemental Analysis with Expansion Data – ICRR/Investigator Judgement	Response evaluable
	Subgroup Analysis for Overall Response Rate Including Supplemental Analysis with Expansion Data – ICRR Judgement	Response evaluable
	Waterfall Plot and Swimlane Plot Including Supplemental Analysis with Expansion Data – ICRR Judgement	Response evaluable
	Summary of Disease Control Rate Including Supplemental Analysis with Expansion Data – ICRR Judgement	Response evaluable
	Summary of Clinical Benefit Rate Including Supplemental Analysis with Expansion Data – ICRR Judgement	Response evaluable
	Summary of Duration of Response Including Supplemental Analysis with Expansion Data – ICRR Judgement	Responders in Response evaluable
	Summary of Time to Response Including Supplemental Analysis with Expansion Data – ICRR Judgement	Responders in Response evaluable
	Summary of Overall Survival and Kaplan-Meier Plot	Treated
	Summary of Progress-Free Survival and Kaplan-Meier Plot – ICRR Judgement	Treated
Safety	Overall Summary of Treatment-emergent Adverse Events (TEAEs)	Treated
	TEAEs by SOC, PT, and Toxicity Grade	Treated
	Related TEAEs by SOC, PT, Toxicity Grade and Study Agent	Treated
	TEAEs of Special Interest by SOC, PT and Toxicity Grade	Treated
	Serious TEAEs by SOC, PT and Toxicity Grade	Treated
	Related Serious TEAEs by SOC, PT, Toxicity Grade and Study Agent	Treated
	TEAEs leading to Discontinuation of Study Agent by SOC, PT and Toxicity Grade	Treated
	Related TEAEs leading to Discontinuation of Study Agent by SOC, PT and Study Agent	Treated
	TEAEs Leading to Dose Reduction or Interruption of Apalutamide by SOC and PT	Treated
	TEAEs Leading to Dose Interruption or Delay of Goserelin by SOC and PT	Treated
	TEAEs Leading to Death by SOC and PT	Treated
	TEAEs of Toxicity Grade 3 or Greater by SOC and PT	Treated
	Related TEAEs of Toxicity Grade 3 or Greater by SOC, PT and Study Agent	Treated

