### **5. EFFICACY**

This study has 1 primary endpoint, 6 secondary endpoints, and exploratory endpoints. A summary of the planned analyses for efficacy endpoints are listed in [Table 3](#), more details can be found in subsequent sections.

At the interim and final analysis, the primary endpoint (ORR) and the secondary endpoints (CBR, DCR, TTR, DOR) will be analyzed based on the data of the response evaluable participants who are evaluated at least 24 weeks after the initiation of study intervention or confirmed disease evaluation before 24 weeks observation respectively. The other secondary endpoints (OS, PFS) will be analyzed using all available data of treated population. The all available data of response evaluable population at the interim and final analysis will be analyzed as supplemental analysis for primary endpoint and secondary endpoints.

A response of PR or CR must be confirmed by repeat assessments  $\geq 4$  weeks from the initial observation. For a response to qualify as stable disease, follow-up measurements must have met the stable disease criteria at least once at a minimum interval  $\geq 6$  weeks after the first dose of study agent.

In addition, unless specify, disease evaluation is based on the independent radiology review (ICRR).

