## **5.4. Sensitivity analysis**

### **5.4.1. Overall Response Rate (ORR) by investigator**

The same analysis of 5.2.1 will be performed using objective response by investigator judgement.

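### Central-review PFS and DOR censor participants whose progression only the investigator calls, and no investigator-based PFS or DOR analysis is planned to show the effect

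*SAP*

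**What the plan says.** **Who dates the event.** SAP section 5 states that, "unless specify, disease evaluation is based on the independent radiology review (ICRR"). SAP Table 2 labels the interim PFS and DOR outputs as ICRR judgement, while the ORR summary is listed for both ICRR and investigator.

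**Who reads scans during the study.** Protocol 8.1 has the investigator assess response. It gives the role of central review as follows: "All participant scans will be submitted to an independent central radiology review for quality assessment and for the primary analysis". Protocol 7.1 requires study intervention to stop at documented RECIST progression and mentions no central confirmation step.

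**Scans after stopping.** Footnote c of the Schedule of Activities (protocol 1.3) says that "radiographic evaluations must be continued until disease progression but prior to subsequent therapy", but only for participants who stop for safety or tolerability. Protocol 7.1 adds one other group: participants treated beyond progression stay on the imaging schedule.

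**Censoring.** For situations other than progression and death, SAP Table 4 (PFS) and Table 6 (DOR) use the same date: "Date of last disease assessment prior to withdrawal of consent to study participation, lost to follow-up, start of subsequent anticancer therapy". Death is an event in both tables.

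**Planned sensitivity analyses.** SAP 5.4.1 says: "The same analysis of 5.2.1 will be performed using objective response by investigator judgement". Section 5.2.1 is the ORR section. SAP 5.3 repeats PFS and OS in the response-evaluable population, which changes the population and not the assessor. SAP 5.1.2 permits censoring sensitivity analyses when judged necessary, but names no rule, endpoint or trigger.

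**The concern.** Kaplan-Meier estimation assumes that a participant censored at a given time has the same outlook as those still under observation at that time. Here a progression call starts the sequence that leads to censoring. The investigator calls progression, treatment stops, mandated imaging ends, and new therapy may begin. If ICRR did not read the same scan as progression, the central-review analysis has no event and no later scan that could supply one.

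To the extent that these participants are closer to true progression than those still at risk, removing them leaves a healthier risk set and lifts the curve. A single-arm study has no comparator in which a similar bias could offset it. At stake is the reading of two descriptive secondary endpoints, PFS and DOR. No planned analysis would let a reader see how much the choice of assessor contributes.

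**Working it through.** **1. The plan's own figures.** The documents give no PFS or DOR effect size, event count or discordance rate. The only computed operating characteristics are in protocol 9.5: type-1 error 1.3% and power 80.5%. With X and Y the responders in the first and second 12 participants, P(success) = P(X ≥ 7) + Σ(x = 2 to 6) P(X = x)·P(Y ≥ 8 − x). This gives 0.0133 at an ORR of 14% and 0.8054 at 40%, so both figures reproduce. Neither depends on how PFS or DOR is censored.

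**2. Inputs for the size.**
- From the Schedule of Activities: scans at Cycles 3, 5, 7, 9, 11 and 13, which is weeks 8, 16, 24, 32, 40 and 48.
- Assumed, not in the documents: exponential time to investigator progression with a 30-week median; a share d of those progressions not called by ICRR (d = 20%, varied from 10% to 30%); no deaths; no treatment beyond progression.

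**3. Reported curve under Table 4.** The chance of no investigator progression over one 8-week interval is q = 2^(−8/30) = 0.8312. At each scan the central event proportion is (1 − d)(1 − q) = 0.8 × 0.1688 = 0.1350, and discordant participants are censored at that scan. At week 48 the reported PFS is (1 − 0.1350)^6 = 0.419.

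**4. What continued scanning would have shown at week 48.**
- *All discordant cases are central progression at the next scan:* q^6 + d(1 − q)q^5 = 0.3299 + 0.2 × 0.1688 × 0.3969 = 0.343.
- *All are investigator over-calls that return to the ordinary hazard:* q^6 + 6d(1 − q)q^5 = 0.3299 + 0.0804 = 0.410.
- *Half of each:* (0.343 + 0.410)/2 = 0.377.

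| Concordance | Reported | All PD at next scan (gap) | Half and half (gap) | All over-calls (gap) |
|---|---|---|---|---|
| 90% | 37.2% | 33.7% (3.6) | 35.3% (1.9) | 37.0% (0.2) |
| 80% | 41.9% | 34.3% (7.6) | 37.7% (4.2) | 41.0% (0.9) |
| 70% | 47.0% | 35.0% (12.0) | 40.0% (7.0) | 45.0% (2.0) |

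Gaps are in percentage points, taken before rounding. Under the next-scan assumption, varying the median from 16 to 40 weeks gives gaps of about 3 points at 90% concordance, 7 to 8 at 80% and 11 to 12 at 70%.

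**5. Effect of the treatment-beyond-progression exception.** Take d = 20%, and suppose 30% of discordant participants keep being scanned and are read as progression at the next scan. From the second scan on, the carried-over group relative to the rest is 0.2 × 0.3 × 0.1688/0.8312 = 0.0122. The event proportion is then (0.1350 + 0.0122)/1.0122 = 0.1454. Reported PFS is 0.8650 × 0.8546^5 = 0.394, so the gap to 34.3% narrows from 7.6 to about 5 points.

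**6. Median.** Under the next-scan assumption at 80% concordance, the comparator at week 32 is q^4 + d(1 − q)q^3 = 0.4774 + 0.0194 = 0.497, which puts its median at 32 weeks. The reported curve is 0.8650^4 = 0.560 at week 32 and 0.484 at week 40, which puts its median at 40. The comparator is below one half by only 0.3 of a point, so the 8-week difference is one scan interval and not a measure of bias.

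**The case against.** The strongest case against has five parts.

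- **Over-calls.** Central review exists partly to correct investigator over-calls. A reader might infer that everyone censored in this way is about to progress. The documents do not show that, and if every discordant case is an over-call the bias is about 1 point. This stands, and it is why a range is given.
- **Not every discordant case is lost.** A reader might infer that scanning always ends. Protocol 7.1 keeps participants treated beyond progression on the imaging schedule, and deaths count as events. This stands and reduces the effect. A discordant case that becomes an event only at death still lengthens PFS, and Tables 4 and 6 do not say which row applies when death follows new therapy.
- **Existing provisions.** SAP 5.1.2 allows censoring sensitivity analyses. SAP 5.4.1, by repeating 5.2.1, would give investigator-based swim lane and spider plots and response listings, from which discordant cases could be found one by one. This stands in part. The first provision is optional and unspecified, and the second yields no PFS or DOR estimate.
- **Precision.** With 24 participants, about 24 × 0.67 × 0.20 = 3.2 discordant cases are expected by week 48. The simulated standard deviation of the week-48 estimate is about 11 points, more than the largest gap at 80% concordance. This limits the weight of the point, but sampling error has no fixed direction and this bias does.
- **The Imaging Manual.** It is not among the documents and might provide for central reading before treatment stops. The protocol and SAP describe no such step.

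**Conclusion.** The concern holds in a limited form. For a living participant with investigator progression that ICRR does not call, Tables 4 and 6 together with footnote c normally lead to censoring at the last assessment. So far as such participants are closer to true progression than the rest of the risk set, ICRR-based PFS and DOR are biased upward. Nothing prespecified would show it.

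For PFS at week 48, the inflation is about 1 to 8 points at an assumed 80% concordance and 30-week median, before allowing for deaths and treatment beyond progression. The concordance, the median and the fate of discordant cases are all assumptions; DOR was not modelled separately.

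Two stronger readings are not supported. One is a shift in median PFS from 32 to 40 weeks, which comes from the scan grid. The other is that the trial's conclusion rests on these endpoints. PFS and DOR are descriptive secondary endpoints, and protocol 9.5 and SAP section 3 base the efficacy and futility decisions on the primary endpoint alone.

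**What to change.** In SAP section 5.4, before database lock, prespecify:

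- (a) investigator-assessed PFS and DOR, using the event and censoring rules of Tables 4 and 6;
- (b) a sensitivity analysis of ICRR PFS and DOR in which investigator progression followed by treatment stop or subsequent therapy counts as an event;
- (c) a table of ICRR against investigator progression calls, so that the discordance rate assumed above is replaced by the observed one.

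The cost is a few extra tables. Investigator responses are already recorded in the eCRF under protocol 8.1, so no new scans or changes in participant management are needed. Analysis (b) may count too many events if the investigator over-calls, so it should be presented as a lower bound beside the ICRR result and not as a replacement for it.

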### 5.3.4. Overall Survival (OS)

#### **Definition**

Overall survival (OS) is defined as the time from the date of the initial dose of study intervention to the date of the participant's death.

#### **Analysis Methods**

Kaplan-Meier estimates will be used for analysis, if there are sufficient data. The censoring method is described in [Table 5](#).

**Table 5: OS Event and Censoring Method**

Situation	Date of Death or Censoring	Outcome
Death	Date of death	OS event
Other (eg, withdrawal of consent to study participation, lost to follow-up, etc.)	Last known date to be alive	Censored

### 5.3.5. Time to response (TTR)

#### **Definition**

Time to response (TTR) is defined among responders (with a CR or PR) as the time between date of the initial dose of study intervention and the first efficacy evaluation that the participant has met all criteria for CR or PR.

#### **Analysis Methods**

Descriptive summary statistics will be provided.

### 5.3.6. Duration of Response (DOR)

#### **Definition**

Duration of response (DOR) will be calculated among responders from the date of initial documentation of a response (CR or PR) to the date of first documented evidence of progressive disease as defined in RECIST version 1.1 or death, whichever occurs first.

## **Analysis Methods**

The DOR will be calculated by the Kaplan-Meier method descriptively in participants who responded. Median DOR and the corresponding 95% CI will be provided if estimable with Kaplan-Meier plot. In addition, swim lane plot will also be provided.

**Table 6: DOR Event and Censoring Method**

Situation	Date of Progression or Censoring	Outcome
Disease progression	Earliest date that indicates disease progression	DOR event
Death	Date of death	DOR event
Other (eg, withdrawal of consent to study participation, lost to follow-up, start of subsequent anticancer therapy etc.)	Date of last disease assessment prior to withdrawal of consent to study participation, lost to follow-up, start of subsequent anticancer therapy	Censored

## **5.4. Sensitivity analysis**

### **5.4.1. Overall Response Rate (ORR) by investigator**

The same analysis of 5.2.1 will be performed using objective response by investigator judgement.

## **6. SAFETY**

All safety analyses will be made on the treated population.

### **6.1. Adverse Events**

The verbatim terms used in the CRF by investigators to identify adverse events (AE) will be coded using the Medical Dictionary for Regulatory Activities (MedDRA). Any AE occurring at or after the initial administration of study agent through the day of last dose plus 30 days is considered to be treatment emergent. If the event occurs on the day of the initial administration of study agent, and either event time or time of administration are missing, then the event will be assumed to be treatment emergent. If the event date is recorded as partial or completely missing, then the event will be considered to be treatment emergent unless it is known to be prior to the first administration of study agent based on partial onset date or resolution date. All reported treatment-emergent adverse events will be included in the analysis. For each adverse event, the number and percentage of subjects who experience at least 1 occurrence of the given event will be summarized.

A summary for tables and listings is shown in [Table 7](#):

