6.5.3. Prohibited Therapy

Concurrent enrollment in another investigational drug or device study is prohibited during the Treatment Phase.

The following medications are prohibited while on study until the end-of-treatment (EOT) visit. For drugs known to lower the seizure threshold or cause seizures, the administration should be avoided for 30 days after last dose of study intervention. The sponsor must be notified in advance (or as soon as possible thereafter) of any instances in which prohibited therapies are administered.

- Chemotherapeutic, biologic, or other agents with antitumor effect against SGC
- Antiandrogens (eg, bicalutamide, flutamide, enzalutamide, abiraterone acetate plus prednisone)
- 5- α reductase inhibitors
- Estrogens
- Progestational agents (eg, cyproterone acetate)
- Androgens

- Spironolactone
- Drugs known to lower the seizure threshold or cause seizures (Section 10.8, Appendix 8)

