7. DISCONTINUATION OF STUDY INTERVENTION AND PARTICIPANT DISCONTINUATION/WITHDRAWAL

7.1. Discontinuation of Study Intervention

For all participants in the study, discontinuation from study intervention will not result in automatic withdrawal from the study. A participant's study intervention must be discontinued if:

- The participant withdraws consent to receive study intervention
- The investigator believes that for safety reasons or tolerability reasons (eg, AE) it is in the best interest of the participant to discontinue study intervention
- The participant becomes pregnant Refer to Section 10.5, Appendix 5, Contraceptive Guidance and Collection of Pregnancy Information
- Noncompliance with continued treatment or procedure requirements that the sponsor considers would impact the study evaluation despite frequent corrective instruction
- Documented radiographic (RECIST version 1.1) disease progression
- More than 2 dose level reductions for treatment-related AEs (Table 1 and Table 2)
- Seizure of any grade or Grade 4 neurotoxicity
- The participant receives concurrent (non-protocol) anticancer treatment

If a participant discontinues study intervention for any reason but does not withdraw consent for follow-up, then the scheduled assessments must be continued according to the follow-up phase in the SoA (Section 1.3). The EOT visit should be conducted within 30 days after the last dose of study intervention. The reason(s) a participant discontinues study intervention will be recorded on the eCRF. Once a participant discontinues treatment with the study intervention, the participant will not be permitted to be retreated.

In instances where the investigator feels a participant may continue to receive clinical benefit from further treatment with study intervention after documented disease progression, the case should be discussed with the sponsor's medical monitor, who in conjunction with the investigator, will determine if treatment beyond RECIST version 1.1 defined progression is indicated. If the participant is treated beyond documented disease progression, disease assessments will continue according to the schedule in Section 1.3 and the investigator and sponsor medical monitor will review clinical benefit after each disease assessment.

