8.3. Adverse Events and Serious Adverse Events

Timely, accurate, and complete reporting and analysis of safety information from clinical studies are crucial for the protection of participants, investigators, and the sponsor, and are mandated by regulatory agencies worldwide. The sponsor has established Standard Operating Procedures in conformity with regulatory requirements worldwide to ensure appropriate reporting of safety information; all clinical studies conducted by the sponsor or its affiliates will be conducted in accordance with those procedures.

Adverse events will be reported by the participant (or, when appropriate, by a caregiver, surrogate, or the participant's legally acceptable representative) for the duration of the study.

For further details on AEs and SAEs (Definitions and Classifications; Attribution Definitions; Severity Criteria; Special Reporting Situations; Procedures) as well as product quality complaints (PQCs), refer to Section 10.4, Appendix 4, Adverse Events: Definitions and Procedures for Recording, Evaluating, Follow-up, and Reporting.

8.3.1. Time Period and Frequency for Collecting Adverse Event and Serious Adverse Event Information

All Adverse Events

All AEs and special reporting situations, whether serious or nonserious, will be reported from the time a signed and dated ICF is obtained until 30 days after the last dose of study intervention. Serious adverse events (SAEs), including those spontaneously reported to the investigator within 30 days after the last dose of study intervention, must be reported using the Serious Adverse Event Form. The sponsor will evaluate any safety information that is spontaneously reported by an investigator beyond the time frame specified in the protocol.

Serious Adverse Events

All SAEs occurring during the study must be reported to the appropriate sponsor contact person by study-site personnel within 24 hours of their knowledge of the event. Also, SAEs that occur after 30 days following the last intervention administration and are considered to be related to the study intervention will be collected and reported to the appropriate sponsor contact person.

Information regarding SAEs will be transmitted to the sponsor using the Serious Adverse Event Form, which must be completed and signed by a physician from the study site, and transmitted to the sponsor within 24 hours. The initial and follow-up reports of an SAE should be made according to the safety monitoring plan.

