9.4.3. Safety Analyses

All safety analyses will be made on the treated population.

Adverse Events

The verbatim terms used in the eCRF by investigators to identify AEs will be coded using the Medical Dictionary for Regulatory Activities (MedDRA). Toxicities will be graded for severity according to NCI-CTCAE, version 5.0. Any AE occurring at or after the initial administration of study intervention through the day of last dose plus 30 days is considered to be treatment-emergent. All reported AEs will be included in the analysis. For each AE, the percentage of participants who experience at least 1 occurrence of the given event will be summarized.

Clinical Laboratory Tests

Laboratory data will be summarized by type of laboratory test. Descriptive statistics will be calculated for all laboratory analyte at baseline and at selected scheduled timepoints. Parameters with predefined NCI-CTCAE toxicity grades will be summarized. Change from baseline to the worst toxicity grade experienced by the participants during the study will be provided as shift tables.

Vital Signs

Descriptive statistics of blood pressure (systolic and diastolic) values and changes from baseline will be summarized.

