#### 2.4. Imputation Rules for Missing AE Date/Time of Onset/Resolution

Treatment-emergent adverse events (TEAEs) for the treatment phase are those events with an onset date/time on or after the start of study intervention through the day of last dose plus 30 days is considered to be treatment -emergent.

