#### **4.6. Prior and Concomitant Medications**

Prestudy and concomitant therapies, other than study treatment, taken prior to starting study treatment and those administered during the study will be summarized. Therapies are considered concomitant if taken during the treatment period (within 30 days of the last study intervention dose). Therapies will be summarized by WHO Drug therapeutic class and generic therapy name.

Summaries of concomitant therapies and prestudy therapies will be presented by ATC term.

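### All-cause TEAE tables can include events that began on the next anticancer therapy, because the window runs to last dose plus 30 days with no flag or cut when that therapy starts

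*SAP*

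**What the plan says.** Three definitions give the same window for treatment-emergent adverse events (TEAEs):

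- SAP 6.1: any event from first administration "through the day of last dose plus 30 days is considered to be treatment emergent".
- SAP 2.4: events with onset "on or after the start of study intervention through the day of last dose plus 30 days".
- Protocol 9.4.3: "Any AE occurring at or after the initial administration of study intervention through the day of last dose plus 30 days is considered to be" a TEAE.

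Collection matches. Under Protocol 8.3.1, AEs "will be reported from the time a signed and dated ICF is obtained until 30 days after the last dose of study intervention".

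Protocol 6.5.3 sets when other anticancer treatment may begin: "The following medications are prohibited while on study until the end-of-treatment (EOT) visit". Its list includes "Chemotherapeutic, biologic, or other agents with antitumor effect against SGC". On the visit itself, Protocol 7.1 says: "The EOT visit should be conducted within 30 days after the last dose of study intervention".

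The efficacy rules do respond to new therapy. ORR, CBR and DCR count only what precedes subsequent therapy (SAP 5.2.1, 5.3.1, 5.3.2). PFS and DOR are censored at the last assessment before it (SAP Tables 4 and 6). The safety section has no counterpart.

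**The concern.** Study treatment ordinarily runs until progression, which is when a next therapy comes into question. If the EOT visit is early and a new agent follows, its toxicity can appear while the TEAE window is still open. The definition then assigns those events to apalutamide plus goserelin in every all-cause table.

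The safety profile is a secondary endpoint (Protocol 3). There is one arm of about 24 participants, so no comparison group shares the contamination, and a single participant moves a percentage noticeably. At stake is how the all-cause incidences are read. The efficacy conclusion is not involved.

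**Working it through.** The plan states no figure on this point, so there is nothing to reproduce. The check sets the rules side by side and then sizes one affected participant.

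**Step 1. Can new therapy start inside the window?** Let day 0 be the last dose.

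| Rule | Ends at | Source |
|---|---|---|
| TEAE window | day 30 | SAP 2.4, SAP 6.1, Protocol 9.4.3 |
| AE collection | day 30 | Protocol 8.3.1 |
| Ban on antitumor agents | EOT visit, any day up to 30 | Protocol 6.5.3, 7.1 |

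Possible overlap = 30 − day of the EOT visit:

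- EOT on day 7: 30 − 7 = 23 days
- EOT on day 14: 30 − 14 = 16 days
- EOT on day 30: 0 days

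Protocol 6.5.3 carries one restriction on to 30 days after last dose, for drugs that lower the seizure threshold. It does not do so for antitumor agents.

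**Step 2. Does another rule remove these events?** The only exception in SAP 6.1 concerns events known to precede first dose. Nothing acts at the late end of the window.

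**Step 3. Which tables are exposed?** SAP Table 7 gives a drug-related version for TEAEs (by SOC and PT, and by grade), serious TEAEs, grade 3 or higher TEAEs, and TEAEs leading to discontinuation. Among the tables that events after the last dose can enter, these have none:

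- overall summary
- grade 3 or higher serious TEAEs
- TEAEs leading to death
- AEs of special interest
- AEs of clinical interest
- TEAEs by time period

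Where a drug-related version exists, the all-cause version beside it still carries the events.

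**Step 4. Size per participant.** The input is a target of about 24 treated (Protocol 1.1). If k participants have their only occurrence of an event after new therapy starts, the incidence rises by k/24:

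- k = 1: 1/24 = 4.2 points
- k = 2: 2/24 = 8.3 points
- k = 3: 3/24 = 12.5 points

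A participant who already had the event on study treatment adds nothing, because incidence counts participants. The documents do not give k.

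**Step 5. What would a bare cut lose?** Protocol 2.2 gives an apalutamide half-life of about 7 days after a single dose. Taking simple exponential decline as an approximation, the fraction remaining is 0.5^(days/7):

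- day 14: 0.5^2 = 25%
- day 30: 0.5^(30/7) = 5%

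Drug is still present for much of the window, so a cut that discarded everything after new therapy could remove real apalutamide toxicity.

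**The case against.** The strongest reply is that the window is a deliberate convention, applied consistently. Definition and collection agree, and over-counting toxicity is the cautious direction. Efficacy rules stop at new therapy so that the drug is not credited with another agent's effect; a safety rule need not mirror them. The half-life supports a full 30 days. Drug-related tables cover the main categories, separately for apalutamide and goserelin. SAP 6.4 reports treatment-related on-study deaths. With about 24 participants, individual events can be traced in listings.

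Much of this stands. It rules out replacing the window with a bare cut, and it limits the problem to the all-cause tables. It does not show that those tables can be read as they are, because nothing in the plan marks which events followed new therapy.

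Four stronger readings are tempting, and the documents do not support them:

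- **Laboratory shift tables are contaminated too.** SAP 6.5 takes the worst grade during treatment. Protocol 9.4.3 refers to the study, but scheduled tests stop at the EOT visit and the ban lasts until that visit. If the protocol is followed, scheduled laboratory data precede new therapy.
- **The total inflation can be projected.** That needs the number who switch within 30 days and their event rate. Neither is in the documents.
- **A safety rate in women is biased.** Female safety is exploratory (Protocol 3), and SAP 6.1 plans only listings for these records.
- **SAP 4.6 contradicts SAP 4.7.** SAP 4.6 says "Therapies are considered concomitant if taken during the treatment period (within 30 days of the last study intervention dose"), while SAP 4.7 summarizes therapy after discontinuation as subsequent. One drug can carry both labels, but that changes no endpoint.

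**Conclusion.** The gap is real and moderate. All three definitions leave the TEAE window open after new anticancer therapy may have begun, and no other rule separates the later events. The all-cause TEAE tables can therefore include toxicity of the next therapy, most awkwardly where SAP Table 7 has no drug-related counterpart.

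The supportable size is 4.2 points per participant whose only occurrence of an event follows new therapy, assuming 24 treated. The effect is conditional on participants starting new therapy before day 30 and having a new event before the window closes. If none do, the tables are unaffected.

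The primary ORR test, its boundaries and its error rates are not involved.

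**What to change.** In SAP 2.4 and 6.1, with matching wording in Protocol 9.4.3:

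1. Flag every AE with onset on or after the first subsequent anticancer therapy.
2. Report the all-cause TEAE tables with the window ending at the earlier of last dose plus 30 days or the day before that therapy.
3. Keep as treatment-emergent any event within 30 days that the investigator relates to study intervention.
4. Do not apply the cut where the therapy start date is fully missing. SAP 4.7 imputes it to the day after discontinuation, which would erase nearly all of that participant's 30-day window. SAP 4.7 can move partially missing dates to the same day, so the SAP should also say how those are handled.
5. List the excluded events and show the full 30-day result alongside. Both readings then stay visible, and the result does not rest only on open-label causality judgements.

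No change to the laboratory tables is needed, and none to treatment, visits or data collection. Subsequent therapy is already recorded in follow-up, and SAP 4.7 already handles its dates.

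The cost is SAP wording, programming and some extra tables. A late event coded as unrelated after new therapy leaves the cut version but remains in the listing and the full-window version.
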